## **12.2 Audits**

The Duke Office of Audit, Risk and Compliance (OARC) office may conduct confidential audits to evaluate compliance with the protocol and the principles of GCP. The PI agrees to allow the OARC auditor(s) direct access to all relevant documents and to allocate his/her time and the time of the study team to the CTQA auditor(s) in order to discuss findings and any relevant issues.

OARC audits are designed to protect the rights and well-being of human research subjects. OARC audits may be routine or directed (for cause). Routine audits are selected based upon risk metrics generally geared towards high subject enrollment, studies with limited oversight or monitoring, Investigator initiated Investigational Drugs or Devices, federally-funded studies, high degree of risk (based upon adverse events, type of study, or vulnerable populations), Phase I studies, or studies that involve Medicare populations. Directed audits occur at the directive of the IRB or an authorized Institutional Official.

OARC audits examine research studies/clinical trials methodology, processes and systems to assess whether the research is conducted according to the protocol approved by the DUHS IRB. The primary purpose of the audit/review is to verify that the standards for safety of human subjects in clinical trials and the quality of data produced by the clinical trial research are met. The audit/review will serve as a quality assurance measure, internal to the institution. Additional goals of such audits are to detect both random and systemic errors occurring during the conduct of clinical research and to emphasize “best practices” in the research/clinical trials environment.

## **12.3 Data Management and Processing**

### **12.3.1 Case Report Forms (CRFs)**

The electronic CRF (eCRF) will be the primary data collection document for the study. The eCRFs will be updated in a timely manner following acquisition of new source data. Only approved study staff (e.g., the PI, the clinical research coordinator, the data management team, and the assistant research practice manager) are permitted to make entries, changes, or corrections in the CRF.

An audit trail will be maintained automatically by the 21 CFR Part 11 compliant electronic CRF management system. Designated personnel will complete user training, as required or appropriate per regulations.

### **12.3.2 Data Management Procedures and Data Verification**

Designated personnel using the electronic CRF will have access based on their specific roles in the protocol as determined by the PRTBTC Data Manager.

Completeness of entered data will be checked automatically by the eCRF system, and users will be alerted to the presence of data inconsistencies. Additionally, the data management team and the statistical team will cross-reference the data to verify accuracy. Missing or implausible data will be highlighted for the PI requiring appropriate responses (i.e. confirmation of data, correction of data, completion or confirmation that data is not available, etc.).

The database will be reviewed and discussed prior to database closure, and will be closed only after resolution of all remaining queries. An audit trail will be kept of all subsequent changes to the data.

### **12.3.3 Study Closure**

Following completion of the studies, the PI will be responsible for ensuring the following activities:

- Data clarification and/or resolution
- Accounting, reconciliation, and destruction/return of used and unused study drugs
- Review of site study records for completeness
- Shipment of all remaining laboratory samples to the designated laboratories

## **13 STATISTICAL METHODS AND DATA ANALYSIS**

All statistical analysis will be performed under the direction of the statistician designated in key personnel. Any data analysis carried out independently by the investigator must be approved by the statistician before publication or presentation.

### **13.1 Analysis Sets**

All patients who receive Evolocumab will be included in summaries of adverse events.

PK and PD analyses will include all patients in the treated and untreated groups who have baseline PK blood collected and underwent a resection.

Analyses of serum and intratumoral levels of Evolocumab will be conducted among treated and untreated patients who were resected or biopsied and had serum collected.

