## 6 OBJECTIVES AND ENDPOINTS

	Objective	Endpoint	Analysis
Primary	Evaluate the pharmacokinetics (PK) of evolocumab and whether it can cross the blood brain barrier (BBB) to accumulate intratumorally in patients with primary and recurrent glioma or glioblastoma	Presence of evolocumab detected in surgical resection or biopsy samples by means of mass spectrometry	See Section 13.4
Secondary	Compare lipid metabolism of tumor cells taken from resected or biopsied samples after dose of evolocumab to resected or biopsied samples obtained from s from untreated glioma patients.	Level of lipid metabolism within the resected or biopsied tumor as assessed via fluorescence-activated cell sorting (FACS)	See Section 13.5.1
Secondary	Compare MHC-I expression on tumor cells following administration of evolocumab to samples from untreated glioma patients with tissue	Extent of MHC-I expression within the resected or biopsied tumor, as assessed by fluorescence-activated cell sorting (FACS)	See Section 13.5.1
Secondary	Among patients treated with evolocumab, describe the strength of the association between serum and intratumoral levels of evolocumab. Peripheral blood samples to be taken before administration of evolocumab and at time of surgery or biopsy.	Correlation of serum and intratumoral levels of evolocumab	See Section 13.5.2 .
Exploratory	Describe the immune characteristics of tumor cells taken from resected or biopsied samples	Sequencing characteristics as assessed by multi-omics analysis, immune infiltration, and T cell profiling	See Section 13.6
Exploratory	Assess the activity of T cells isolated from tumor specimens in patients treated with or without evolocumab	Characterization of tumor-infiltrating lymphocytes (TILs) based on flow cytometry immunostaining of TILs for expression of markers of exhaustion (e.g., PD-1, Lag3, TIM3) and activation (CD137)	See Section 13.6

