## 9 SUBJECT ELIGIBILITY

### 9.1 Inclusion Criteria

#### Both arms:

1. Adult patients  $\geq 18$  years old
2. Newly diagnosed or recurrent glioma or glioblastoma (GBM) (if recurrent, prior pathology report indicating glioma)
3. A clinical indication for gross macroscopic resection, debulking of the glioma, or biopsy, with sufficient tumor size that can allow collection of specimens for the required analyses.

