## 10.4 Active Follow-up Period

### Days 4-14 – Surgical resection or biopsy

- Tumor tissue collection (applies to patients who consent to either arm of the study) – this tissue will be taken intraoperatively for pharmacokinetic LC-MS analysis to assess for the presence of evolocumab.
  - Sample will only be taken for analysis if greater than 20 mg of resected or biopsied tissue available (excess available beyond that required for histological analysis)
  - Sample to be aliquoted into 25 mg sections for resections and 10-20 mg (1-2 cores) for biopsies

Treatment arm only:

- Pharmacokinetic blood draw (5 mL, drawn at time of surgery or biopsy, i.e., PK draw may occur either immediately before or during surgery or biopsy)Error! Bookmark not defined.
- Adverse events monitoring

About 2 weeks following surgery or biopsy (treatment arm only)

- Physical and neurological exam
- Laboratory evaluations (obtained as part of standard post-operative labs)
  - CBC with differential
  - CMP
- Adverse events monitoring

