#### **13.5.1 Key Secondary Objectives #1and #2: Lipid Metabolism and Tumor Cells Expressing MHC-I**

The first two secondary objectives involve a comparison of the pharmacodynamics (PDs) of Evolocumab in treated patients relative to that observed in a control cohort of untreated patients. The characterization of the PD properties will include the following: (1) Lipid metabolism of tumor cells taken from resected or biopsied samples, and (2) Analysis of tumor cells expressing MHC-I will be performed by fluorescence-activated cell sorting (FACS). Analyses similar to those describe for the primary objective will be performed.

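### Section 13.1 admits only resected patients to the PK and PD analyses, so a biopsied patient with adequate tissue would leave the lipid-metabolism and MHC-I comparisons without being replaced

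*Combined protocol and SAP*

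**What the plan says.** Section 13.1 defines three sets. The first, for adverse events, is everyone who receives evolocumab. The second reads: "PK and PD analyses will include all patients in the treated and untreated groups who have baseline PK blood collected and underwent a resection". The third covers serum and intratumoral evolocumab levels and is drawn from "among treated and untreated patients who were resected or biopsied and had serum collected".

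Elsewhere the plan includes biopsy:

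- **Section 9.1, both arms:** "A clinical indication for gross macroscopic resection, debulking of the glioma, or biopsy".
- **Section 6, secondary endpoints:** "Level of lipid metabolism within the resected or biopsied tumor" and "Extent of MHC-I expression within the resected or biopsied tumor".
- **Section 10.4, tissue handling:** "Sample to be aliquoted into 25 mg sections for resections and 10-20 mg (1-2 cores) for biopsies".
- **Section 13.5.1, pharmacodynamic objectives:** "Lipid metabolism of tumor cells taken from resected or biopsied samples", with MHC-I analysed alongside it.
- **Sections 13.4.1 and 13.4.2:** the primary variable and the treated-versus-control comparison are both defined on tumour that was either resected or biopsied.

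Section 10.8.3 replaces patients withdrawn before the baseline draw and injection, treated patients who have neither surgery nor biopsy, and patients without enough tissue. Having a biopsy rather than a resection is not a reason for replacement.

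**The concern.** The section that fixes who is analysed disagrees with the sections that fix who is enrolled, what is measured and what is compared. Resection cannot safely be read as shorthand for any procedure, because the next sentence of 13.1 names resection and biopsy separately.

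The consequence falls on the two pharmacodynamic comparisons. The third sentence of 13.1 brings biopsied patients back for evolocumab levels only. Nothing in 13.1 brings them back for lipid metabolism or MHC-I. Section 7.4, despite its title, gives no evaluability rule for these endpoints, and Section 13.4.3 marks the handling of missing values as not applicable.

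With at most 10 treated patients, each one lost matters. Sections 3.3 and 7.1 describe the controls as undergoing craniotomy, so the loss may fall mainly on the smaller arm.

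**Working it through.** **Step 1: follow one patient through the plan.** Take a treated patient who has the baseline draw, receives the injection, and has a biopsy with more than the 20 mg that Section 10.4 requires.

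| Place | Status of this patient |
|---|---|
| 9.1, criterion 3 | Eligible |
| 10.4 | Tissue collected, with a biopsy-specific aliquot size |
| 6 and 13.5.1 | Contributes to lipid metabolism and MHC-I |
| 13.4.1 and 13.4.2 | Contributes to the primary comparison |
| 13.1, third sentence | In the set for serum and intratumoral levels |
| 13.1, second sentence | Not in the PK and PD set |
| 10.8.3 | Not replaced: had a biopsy and gave enough tissue |

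For lipid metabolism and MHC-I, the second sentence of 13.1 is the only analysis-set rule, and it leaves the patient out.

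**Step 2: size of the loss.** The plan has no power or precision figure to reproduce. Section 13.8 bases the sample size on practical considerations and calls the purpose descriptive. Precision is therefore the natural measure, and it needs no assumed effect.

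Inputs from the documents: up to 10 treated and up to 20 controls (Section 7.1). Assumptions: *b* treated patients are biopsied, all 20 controls are resected, the two groups share a common SD, and a two-sample t interval is used. The treated number is n = 10 − b.

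Half-width of the 95% confidence interval, in SD units = t(0.975, n + 18) × √(1/n + 1/20)

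| b | n | t | √(1/n + 1/20) | Half-width (SD) | Increase over n = 10 |
|---|---|---|---|---|---|
| 0 | 10 | 2.048 | 0.387 | 0.79 | – |
| 1 | 9 | 2.052 | 0.401 | 0.82 | 4% |
| 2 | 8 | 2.056 | 0.418 | 0.86 | 8% |
| 3 | 7 | 2.060 | 0.439 | 0.90 | 14% |
| 5 | 5 | 2.069 | 0.500 | 1.03 | 30% |

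**Step 3: why this is an upper bound.** The table assumes that every biopsied patient would otherwise supply flow-cytometry data. Section 3.3 uses 20 to 100 mg of tumour per patient for mass spectrometry. Footnote 5 to Table 4 expects a little over 20 mg from a biopsy. Mass spectrometry alone could use up a small biopsy, and such a patient would be missing from the pharmacodynamic comparisons whatever 13.1 said.

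**The case against.** The best defence is that the intent is plain. The endpoint table and Sections 13.4 and 13.5.1 name biopsy. The version 5.0 amendment summary says that biopsy language was extended through several sections, Section 13 among them. Section 10.8.3 treats a biopsied patient with enough tissue as not needing replacement, which implies that the patient counts. The sentence in 13.1 also says that all resected patients are included and does not add the word only. On this view a sensible analyst would include the biopsies, and no harm follows.

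The point about intent stands: this is most likely a missed edit. It does not remove the defect, because an analysis-set definition works by stating who is in, and this one leaves biopsied patients out. The objection that the size is hypothetical also stands, since the documents give no biopsy fraction and claim no power.

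A reader might go further and infer that the primary analysis is restricted to resections, or is open to two equally valid readings. Section 6 does give the primary objective a pharmacokinetic label ("Evaluate the pharmacokinetics (PK) of evolocumab and whether it can cross the blood brain barrier (BBB) to accumulate intratumorally"), which brings the second sentence of 13.1 into play. But Sections 13.4.1 and 13.4.2 define the primary variable and comparison on resected or biopsied tumour, and the third sentence of 13.1 agrees for intratumoral levels. A resection-only primary analysis would contradict 13.4.

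A reader might also infer that the baseline-blood condition would exclude biorepository controls. That would follow only if those specimens came without blood, which the documents do not say. Consented patients in both arms have a baseline draw scheduled (Sections 7.4 and 10.3).

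**Conclusion.** The inconsistency is certain from the text. It affects chiefly the lipid-metabolism and MHC-I comparisons: as written, dosed and biopsied patients with adequate tissue are excluded and not replaced. For the primary comparison, the second sentence of 13.1 only needs to be made to agree with 13.4 and with the sentence that follows it.

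The size is unknown. It is zero if no treated patient has a biopsy. With 3 or 5 biopsies among 10, both assumed, the interval for the treated-control difference widens by at most 14% or 30%. These figures rest on 20 resected controls and a common SD, and they do not apply to the primary endpoint. The point deserves correction because the error lies in the governing definition and costs almost nothing to remove before analysis.

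**What to change.** In the second sentence of Section 13.1, replace the condition of having had a resection with having had a resection or biopsy with evaluable tissue. This brings it into line with Sections 6, 13.4 and 13.5.1. Leave the baseline-blood condition as it is.

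While the section is open, limit the set for the serum-tumour correlation to treated patients with serum and tumour samples from the time of the procedure. The third sentence of 13.1 currently includes untreated patients, whereas Section 13.5.2 describes the association among treated patients only.

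The cost is two sentences of wording, with no new patients, samples or assays. The change should be made before the data are analysed.

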#### **Secondary Objectives:**

1. Among patients treated with evolocumab, assess the association between serum and intratumoral levels of evolocumab in the patients treated with evolocumab.
2. Compare the PDs of evolocumab in treated patients relative to that observed in a control cohort of untreated patients. The characterization of the PD properties will include the following:
  - a. Lipid metabolism of tumor cells taken from resected or biopsied samples
  - b. Analysis of tumor cells expressing MHC-I will be performed by fluorescence-activated cell sorting (FACS)

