#### **13.5.2 Secondary Objective #3: Serum and Intratumoral Levels of Evolocumab**

Among patients treated with evolocumab, the third secondary objective is an assessment of the relationship between serum and intratumoral levels of the drug. These assessments will be obtained at the time of surgical procedure. A scatterplot will graphically show the relationship between these two measures. Spearman's rank correlation will assess their association.

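### The analysis sets in Section 13.1 do not match the analyses they serve: untreated patients appear in the serum–tumour set, and biopsied patients drop out of the PK and PD set

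*Combined protocol and SAP*

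**What the plan says.** Section 13.1 defines three sets, one per paragraph. The first, for adverse events, is not at issue.

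- Paragraph two covers PK and PD analyses. It takes patients from both groups "who have baseline PK blood collected and underwent a resection".
- Paragraph three reads "Analyses of serum and intratumoral levels of Evolocumab will be conducted among treated and untreated patients", with the further condition "who were resected or biopsied and had serum collected".

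Three other places give the population for the serum–tumour association:

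- Section 3.1, secondary objective 1: "Among patients treated with evolocumab, assess the association between serum and intratumoral levels of evolocumab in the patients treated with evolocumab".
- Section 6, objectives table: "Among patients treated with evolocumab, describe the strength of the association between serum and intratumoral levels of evolocumab".
- Section 13.5.2: "Among patients treated with evolocumab, the third secondary objective is an assessment of the relationship between serum and intratumoral levels of the drug". This section also names the scatterplot and Spearman's rank correlation, and adds "These assessments will be obtained at the time of surgical procedure".

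For the comparisons between cohorts, Section 13.4.2 compares the intratumoral level in treated and control patients after resection or biopsy. Section 13.5.1 applies similar analyses to the PD measures, on the same kinds of sample. Neither makes blood a condition. Section 7.1 and inclusion criterion 3 in Section 9.1 allow biopsy. Sections 3.3, 7.1 and 13.3 allow controls to be drawn from the tissue biorepository.

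**The concern.** An analysis-set section exists to say who enters each analysis. Two of the three paragraphs here do not fit the analyses they appear to describe.

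Paragraph three uses the words of the 13.5.2 heading, and no other planned analysis uses serum and tumour levels together. It therefore reads most naturally as the set for the correlation, yet it includes undosed patients. If controls were pooled in, the coefficient would partly measure who received drug, rather than whether serum level tracks tumour level among those who did.

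Paragraph two, read literally, removes biopsied patients from the primary and PD comparisons, along with any control without baseline study blood. In a trial of up to 10 treated patients and 20 controls, each such exclusion counts. Under Section 10.8.3 a patient is replaced for having no procedure or too little tissue. A biopsied patient with enough tissue would therefore use a place, fall outside the paragraph-two set and not be replaced.

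**Working it through.** The plan states no correlation target, power or alpha, so there is no figure of its own to reproduce. The check has two parts.

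**1. What pooling would do to the coefficient**

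Inputs from the documents: 10 treated patients and up to 20 controls (Section 7.1); Spearman's coefficient (Section 13.5.2).

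Assumed, because the documents do not give them:

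- *m* controls have serum, and all are tied at background, below every treated serum value.
- Drug is detected in *d* of the 10 treated tumours. All other tumour values, treated and control, are tied lowest.
- Serum and tumour levels are unrelated among the treated.

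Write N = m + 10 and S(k) = k(k² − 1)/12.

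- Serum ranks: SSx = S(N) − S(m).
- Tumour ranks: SSy = S(N) − S(N − d).
- Mean rank deviations in serum are +m/2 (treated) and −5 (controls). In tumour they are +md/20 and −d/2.
- Expected cross-product = 10 × (m/2)(md/20) + m × 5 × (d/2) = mdN/4.
- Expected rho = (mdN/4) / √(SSx × SSy).

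For m = 20: S(30) = 2247.5 and S(20) = 665, so SSx = 1582.5.

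- d = 10: SSy = 1582.5; rho = 1500/1582.5 = 0.95.
- d = 5: SSy = 2247.5 − 1300 = 947.5; rho = 750/√(1582.5 × 947.5) = 0.61.
- d = 1: SSy = 2247.5 − 2030 = 217.5; rho = 150/√(1582.5 × 217.5) = 0.26.
- d = 0: every tumour value ties, SSy = 0, and rho is undefined.

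With fewer controls having serum:

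- m = 10 (SSx = 582.5): 500/582.5 = 0.86 for d = 10; 250/√(582.5 × 385) = 0.53 for d = 5; 50/√(582.5 × 95) = 0.21 for d = 1.
- m = 5 (SSx = 270): 187.5/270 = 0.69; 93.75/√(270 × 197.5) = 0.41; 18.75/√(270 × 52.5) = 0.16.
- m = 0: nothing is pooled. Expected rho is 0, with a simulated 95% range of about −0.64 to 0.65 for 10 patients.

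Two checks on how far this depends on the assumptions:

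- If the serum and tumour orders among the treated were exactly reversed (m = 20, d = 10), the within-treated part is −82.5, and rho is still (1500 − 82.5)/1582.5 = 0.90.
- If background values are untied assay noise instead, both sums of squares are 2247.5. Rho for m = 20 is then 1500/2247.5 = 0.67, 750/2247.5 = 0.33 and 150/2247.5 = 0.07 for d = 10, 5 and 1. It averages about 0 if treated tumours contain only noise.

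**2. Paragraph two against the analyses it covers**

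- Procedure: 13.1 paragraph two requires resection; 13.4.2 and 13.5.1 take resection or biopsy.
- Blood: 13.1 paragraph two requires a baseline PK draw; 13.4.2 and 13.5.1 do not.
- Effect: if *b* of 10 treated patients are biopsied, 10 − b remain. If *k* of 20 controls are repository specimens without study blood, at most 20 − k remain. The documents give neither *b* nor *k*.

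**The case against.** The strongest reply is that there is little real conflict. The treated-only limit stands in three places, and the method is set out in full only in 13.5.2, under that limit. Paragraph three of 13.1 speaks of levels, not of association. A broad set in 13.1 and a narrower population in 13.5.2 can coexist, since Section 10.9.3 tests serum and tumour in both arms. The coefficient is descriptive, no decision rests on it, and the planned scatterplot would probably show two clusters. Most of this stands, and it is why the point is minor. It does not make 13.1 right: if paragraph three is meant for the cohort comparison of levels, it adds a serum condition that 13.4.2 lacks.

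For paragraph two, one can say that resection is loose wording for any tissue procedure. That may be the intent, but paragraph three of the same section names both procedures.

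A reader might infer more than the documents support:

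- *That the plan pools the cohorts.* It does not clearly do so; 13.5.2 is specific and probably governs.
- *That pre-dose serum could enter the correlation.* Section 13.5.2 fixes the timing. Section 10.4 has the treatment-arm sample "drawn at time of surgery or biopsy, i.e., PK draw may occur either immediately before or during surgery or biopsy", and a footnote to Table 4 gives comparison with the tumour level as its purpose.
- *That the synopsis leaves the Spearman population open.* Section 3.6 is silent on it, but Section 3.1 of the same synopsis states it.
- *That repository controls have no blood.* The documents do not say either way.

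**Conclusion.** The point holds as a minor inconsistency. Section 13.1 assigns dosed and undosed patients to analyses of serum and tumour levels, while the objectives and 13.5.2 keep the association to dosed patients. It also applies resection and blood conditions to cohort comparisons that are defined without them.

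The pooled coefficients of 0.95, 0.61 and 0.26 are conditional on someone using the 13.1 set for the correlation. They further assume no association among 10 treated patients, 20 controls with serum tied at background, and detection in 10, 5 or 1 treated tumours. Whether drug is detectable at all is the primary question, so the low end matters as much as the high end. The effect shrinks with fewer serum-bearing controls or with untied background values.

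The size of the paragraph-two problem depends on how many patients are biopsied and how many controls lack blood, which cannot be known from the documents. No stated figure in the plan is wrong.

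**What to change.** Three wording changes in Section 13.1:

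- (a) Replace paragraph three with: *The correlation in 13.5.2 uses only treated patients who have a tumour specimen and serum from the time of the procedure. Control values do not enter it.*
- (b) Replace paragraph two with: *The between-cohort comparisons of intratumoral level (13.4.2) and of the PD measures (13.5.1) include every treated or control patient with a resection or biopsy and the relevant tumour result, whether or not blood was collected.*
- (c) Add: *Control serum levels, where available, are summarised by arm only.*

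Paragraphs two and three need changing together. If only the third is corrected, the resection condition in the second would still conflict with the PD comparisons, and with the biopsied patients whom (a) admits to a PK analysis.

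The cost is a short amendment to one section. No new samples, visits or assays are needed.
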